## **7. Treatment[s]**

### **Treatments to be administered**

All patients will receive regorafenib 120mg daily for 3 weeks on and 1 week off with cycle 1. Dose escalation to 160mg will be permitted after the first cycle at the discretion of the treating physician. Subjects will continue study treatment until disease progression or other reasons for removal from treatment (section6).

### **Treatment assignment**

#### **Regorafenib**

Regorafenib tablets will be packaged in high density polyethylene bottles with a white child resistant closure and induction seal. Each bottle includes 28 tablets and a 3-gram desiccant. The bottles will have a label affixed containing study identification, product identification, and quantity of tablets. Once the drug has been received it must be kept in a secure, dry location. Study drug must be stored in its original bottle at a temperature not above 25°C (77°F).

The study drug must be exclusively used for the investigation specified in this protocol and it will only be accessible to authorized staff.

### Study Treatment

The initial screening period is 14 days from the date of consent. Once approved, by the coordinating site, an additional 14 day period is granted for scheduling, in which subjects must start treatment.

Regorafenib will be administered as monotherapy during the study. 120 mg qd (starting dose) will be administered for 3 weeks on /1 week off. One cycle is 28 days. Study treatment must be initiated within 14 days of registration.

Three 40-mg regorafenib tablets (starting dose) should be taken once a day with approximately 8 fluid ounces (240 mL) of water after a low-fat (<30% fat) meal. Some examples of low fat meals are:

- Two slices of white toast with 1 tablespoon of low-fat margarine and 1 tablespoon of jelly and 8 ounces (240 mL) of skim milk (approximately 319 calories and 8.2 g of fat).
- One cup of cereal (i.e. Special K), 8 ounces (240 mL) of skim milk, one piece of toast with jam (no butter or marmalade), apple juice, and one cup of coffee or tea (2 g fat, 17 g protein, 93 g of carbohydrate, 520 calories).

### Dose Modification Levels

The starting dose of regorafenib is 120 mg once daily. Study medication will be administered on a 3 weeks on/1 week off schedule [3 weeks out of every 4].

Dose escalation to 160mg is recommended after the first cycle (4 weeks) at the discretion of the treating physician.

Doses will be held or reduced for clinically significant hematologic and non-hematologic toxicities that are related to protocol therapy according to the guidelines shown in the Dose Delays/Dose Modifications tables that follow. Doses held for toxicity will not be made up but will be counted as missed doses. Dose modifications will follow predefined dose levels. Sites may also follow their institutional practice for dose modifications. Missed doses are to be omitted rather than made up. Dose adjustments for hematologic toxicity are based on the blood counts obtained in preparation for the day of treatment.

The modifications of regorafenib will follow the following predefined dose levels:		
Dose level +1	160mg po qd	Four 40-mg tablets of regorafenib
Dose level 0 (starting dose)	120 mg po qd	Three 40-mg tablets of regorafenib
Dose level - 1	80 mg po qd	Two 40-mg tablets of regorafenib
Dose level - 2	40 mg po qd	One 40-mg tablets of regorafenib

If a subject experiences more than one toxicity, dose reduction should be according to the toxicity with the highest grade.

In the case of two or more toxicities of the same grade, the investigator may dose reduce according to that deemed most causally related to study treatment.

If a dose reduction has been performed, intra-subject dose re-escalation can be considered (up to the maximal 160 mg daily dose) at the discretion of the treating physician provided that the toxicity(ies) has resolved to baseline.

The following tables outline dose adjustments for toxicities related to study drug other than diarrhea, hand-foot skin reaction, hypertension and liver function test abnormalities. More information on dose reductions for diarrhea, hand-foot skin reaction, hypertension, and liver function test abnormalities follows Table 7-1.

Table 7-1: Recommended dose modification for toxicities except diarrhea, hand-foot-skin reaction, hypertension and ALT/ST/bilirubin			
NCI-CTCAE v4.0a	Dose Interruption	Dose Modificationb	Dose for Subsequent Cycles
Grade 0-1	Treat on time	No change	No change
Grade 2 c	Treat on time	No change	No change
Grade 3	Hold until ≤ Grade 2 c	Reduce by 1 dose level	If toxicity remains < Grade 2, dose re-escalation can be considered at the discretion of the treating investigator. If dose is re-escalated and toxicity (≥ Grade 3) recurs, institute permanent dose reduction.
Grade 4	Hold until ≤ Grade 2 c	Reduce by 1 dose level. Permanent discontinuation can be considered at treating investigator's discretion.	

a. NCI-CTCAE = National Cancer Institute - Common Terminology Criteria for Adverse Events, version 4.0  
b. Excludes alopecia, non-refractory nausea/vomiting, non-refractory hypersensitivity, and non-clinically significant and asymptomatic laboratory abnormalities.  
c. If subject is experiencing multiple grade 2 toxicities, treatment can be interrupted at discretion of treating oncologist until toxicities are ≤ grade 1 and then resumed at reduced dose (by 1 level)  
d. If no recovery after a 4 week delay, treatment should be permanently discontinued unless subject is deriving clinical benefit.

In addition to these recommended dose modifications, subjects who develop diarrhea, mucositis, anorexia or other events predisposing to fluid loss or inadequate fluid intake should be carefully monitored and rehydrated as clinically necessary in order to minimize the risk of postural hypotension and renal failure.

## 8. Prevention/Management Strategies for Diarrhea, Hand-Foot Skin Reaction, Hypertension, and Liver Function Test Abnormalities

### Diarrhea

Diarrhea can be a common side effect of regorafenib. The preventive/management strategies for diarrhea should be consistent with local standards (e.g., anti-diarrheals and optimized hydration status).

Anti-diarrhea medications may be introduced if symptoms occur. Previous trials have shown that diarrhea can be managed with loperamide. The recommended dose of loperamide is 4 mg at first onset, followed by 2 mg every 2 to 4 hours until diarrhea-free for 12 hours.

### Hand-Foot Skin Reaction

	Grade 1	Grade 2	Grade 3
NCI-CTCAE v4.0 Palmar-plantar erythrodysesthesia syndrome	Minimal skin changes or dermatitis (e.g., erythema, edema, or hyperkeratosis) without pain	Skin changes (e.g., peeling, blisters, bleeding, edema, or hyperkeratosis) with pain	Severe skin changes (e.g., peeling, blisters, bleeding, edema, or hyperkeratosis) with pain
Further description / examples of skin changes	Numbness, dysesthesia / paresthesia tingling, painless swelling, or erythema of the hands and/or feet	Painful erythema and swelling of the hands and/or feet	Moist desquamation, ulceration, blistering, or severe pain of the hands and/or feet
Effect on activities	Does not disrupt normal activities	Limiting instrumental activities of daily life (e.g., preparing meals, shopping for groceries or clothes, using the telephone, managing money)	Limiting self-care activities of daily life (e.g., bathing, dressing and undressing, feeding self, using the toilet, taking medications) and not bedridden
a. Palmer-plantar erythrodysesthesia syndrome is a disorder characterized by redness, marked discomfort, swelling, and tingling in the palms of hands or the soles of the feet.			

**Table 8-2 Recommended dose modification for hand-foot-skin reactiona**

Grade of event (NCI-CTCAE v4.0)	Occurrence	Suggested Dose Modification
Grade 1	Any	Maintain dose level and reinforce supportive measures for symptomatic relief
Grade 2	1 st occurrence	Interrupt therapy until toxicity resolves to Grade 0-1. b, c When resuming treatment, treat at reduced dose level.
	2 nd occurrence	Interrupt therapy until toxicity resolves to Grade 0-1. b, c When resuming treatment, treat at reduced dose level.
	3 rd occurrence	Discontinue therapy
Grade 3	1 st occurrence	Interrupt therapy for a minimum of 7 days until toxicity resolves to Grade 0-1. c When resuming treatment, decrease dose by one dose level. b, d
	2 nd occurrence	Discontinue treatment permanently

a. More conservative management is allowed if judged medically appropriate by the investigator.  
b. If toxicity returns to Grade 0-1 after dose reduction, dose re-escalation is permitted at the discretion of the investigator if subject has completed one cycle at reduced dose without recurrence of event.  
c. If there is no recovery after a 4-week delay, treatment with regorafenib will be discontinued permanently.  
d. Subjects requiring > 2 dose reductions should go off protocol therapy.  
e. The maximum daily dose is 160 mg.

**At first occurrence of HFSR, independent of grade, prompt reinforcement of supportive measures such as topical emollients, low potency steroids, or urea-containing creams should be administered.**

Recommended prevention/management strategies for skin toxicities consistent with HFSR are summarized below:

### Control of calluses

Before initiating treatment with regorafenib:

- Check condition of hands and feet.
- Suggest a manicure/pedicure, when indicated.
- Recommend pumice stone use for callus or 'rough spot' removal.

During regorafenib treatment:

- Avoid pressure points.
- Avoid items that rub, pinch or create friction.

### Use of creams

- Non-urea based creams may be applied liberally.
- Keratolytic creams (e.g. urea-based creams, salicylic acid 6%) may be used sparingly and only to affected (hyperkeratotic) areas.

- Alpha hydroxyl acids (AHA) based creams may be applied liberally 2 times a day. Approximately 5% to 8% provides gentle chemical exfoliation.
- Topical analgesics (e.g. lidocaine 2%) are to be considered for pain control.
- Topical corticosteroids like clobetasol 0.05% should be considered for subjects with Grade 2 or 3 HFSR. Avoid systemic steroids.

**Tender areas should be protected as follows:**

- Use socks/gloves to cover moisturizing creams
- Wear well-padded footwear
- Use insole cushions or inserts (e.g. silicon, gel)
- Foot soaks with tepid water and Epson salts

**Hypertension**

Hypertension is a known AE associated with regorafenib treatment. Subject will have their blood pressure measured weekly during the first 8 weeks of treatment (either in the office or with nursing services).

If additional blood pressure measurements are done outside the study site, and the blood pressure is > 140 mm Hg systolic or > 90 mm Hg diastolic (NCI CTCAE v4.0), then the subject must contact study personnel.

The management of hypertension, including the choice of antihypertensive medication, will be performed according to local standards and to the usual practice of the investigator. Every effort should be made to control blood pressure by medical means other than study drug dose modification. If necessary, Table 8-4 outlines suggested dose reductions.

Table 8-3: Management of Treatment-Emergent Hypertension		
Grade (CTCAE v4.0)	Antihypertensive Therapy	Regorafenib Dosing

1
 
Prehypertension (systolic BP 120 - 139 mmHg or diastolic BP 80 - 89 mmHg)
	None	
 
• Continue regorafenib
 
• Consider increasing blood pressure (BP) monitoring
 

2
 
Systolic BP 140 - 159 mmHg or diastolic BP 90 - 99 mmHg, OR Symptomatic increase by > 20 mmHg (diastolic) if previously within normal limits
	
 
• Treat with the aim to achieve diastolic BP ≤ 90 mm Hg:
 
• If BP previously within normal limits, start anti-hypertensive monotherapy
 
• If patient already on anti-hypertensive medication, titrate up the dose.
 
	
 
• Continue regorafenib
 
• If symptomatic, hold regorafenib until symptoms resolve AND diastolic BP ≤ 90 mm Hga. When regorafenib is restarted, continue at the same dose level.
 


3
 
Systolic BP ≥ 160 mmHg or diastolic BP ≥ 100 mmHg OR More than one drug or more intensive therapy than previously used indicated
	
Treat with the aim to achieve diastolic BP ≤ 90 mm Hg: Start anti-hypertensive medication
 
AND/OR Increase current anti-hypertensive medication
 
AND/OR Add additional anti-hypertensive medications.
	
 
• Hold regorafenib until diastolic BP ≤ 90 mm Hg, and if symptomatic, until symptoms resolve.a
 
• When regorafenib is restarted, continue at the same dose level.
 
• If BP is not controlled with the addition of new or more intensive therapy, reduce by 1 dose level.b
 
• If Grade 3 hypertension recurs despite dose reduction and antihypertensive therapy, reduce another dose level.c
 

4
 
Life-threatening consequences (eg, malignant hypertension, transient or permanent neurologic deficit, hypertensive crisis)
	Per institutional guidelines	Discontinue therapy

a. Patients requiring a delay of >4 weeks should go off protocol therapy
 
b. If BP remains controlled for at least one cycle, dose re-escalation permitted per investigator's discretion.
 
c. Patients requiring >2 dose reductions should go off protocol therapy.
		

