### Liver Function Abnormalities

For patients with observed worsening of liver tests considered related to regorafenib (i.e. where no alternative cause is evident, such as post-hepatic cholestasis or disease progression), the dose modification and monitoring advice in Table 8-5 should be followed.

Regorafenib is a UGT1A1 inhibitor. Mild, indirect (unconjugated) hyperbilirubinemia may occur in patients with Gilbert’s syndrome.

Table 8-4: Dose Modification/interruption for alanine aminotransferase and/or aspartate aminotransferase increases related to study drug

Increases in ASL/ALT (per NCI-CTCAE v 4.0)	1st Occurrence	Restart	Recurrence
AST and/or ALT < 5 X ULN (<Grade 3)	Continue dosing, with weekly monitoring of liver function until transaminases return to < 3 X ULN (< Grade 1) or baseline.		
ALT and/or AST > 5 X ULN (> Grade 3)	Interrupt dosing, with weekly monitoring until transaminases return to < 3 X ULN or baseline.	If the potential benefit of reinitiating regorafenib is considered to outweigh the risk of hepatotoxicity: reduce 1 dose level and measure transaminases weekly for at least 4 weeks.	Discontinue
ALT and/or AST > 20 X ULN (> Grade 4)	Discontinue		
ALT and/or AST > 3 X ULN (> Grade 2) with concurrent bilirubin > 2 X ULN	Discontinue treatment and measure transaminases weekly until resolution. Exception: subjects with Gilbert's syndrome who develop elevated transaminases should be managed as per the recommendations outlined above for ALT/AST elevations.		

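### Table 8-3 can start the Grade 3 hypertension hold on systolic pressure alone but releases it on diastolic pressure alone, so the hold has no required duration in asymptomatic isolated systolic hypertension

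*Combined protocol and SAP*

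**What the plan says.** Everything at issue is in the Grade 3 row of Table 8-3, in Section 8 of the protocol under Hypertension.

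- **Entry.** Grade 3 is reached at "Systolic BP ≥ 160 mmHg or diastolic BP ≥ 100 mmHg", or when more than one drug or more intensive treatment is needed. Either pressure is enough by itself.
- **Treatment aim.** "Treat with the aim to achieve diastolic BP ≤ 90 mm Hg: Start anti-hypertensive medication". Increasing or adding drugs are the other listed options.
- **Hold and release.** "Hold regorafenib until diastolic BP ≤ 90 mm Hg, and if symptomatic, until symptoms resolve". Dosing then restarts at the same level.
- **Step-down.** "If BP is not controlled with the addition of new or more intensive therapy, reduce by 1 dose level". A recurrence of Grade 3 despite this brings a further reduction.
- **Footnotes.** A delay of more than 4 weeks takes the patient off protocol therapy (footnote a). Footnote b reads "If BP remains controlled for at least one cycle, dose re-escalation permitted", at the investigator's discretion.

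The Grade 2 row covers "Systolic BP 140 - 159 mmHg or diastolic BP 90 - 99 mmHg". Patients in that range without symptoms continue dosing.

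**The concern.** A hold should end when the condition that started it has resolved. Here one of the two pressure triggers is systolic, while the release looks only at diastolic pressure. Where systolic pressure is high and diastolic pressure is not, and there are no symptoms, the hold asks for nothing.

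This is a safety rule for a known adverse event of the drug, in a trial limited to patients aged 65 and over. The stake is a restart at full current dose while the patient is still Grade 3. The decision then depends on the clinician supplying a systolic criterion that the table does not give, which may differ across the four participating sites.

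Scheduled follow-up cannot be relied on to catch an early restart quickly. Beyond cycle 4, footnote b of the Table of Assessments sets visits every 4 weeks, that is 4 × 7 = 28 days apart.

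**Working it through.** The plan states no figure on this point, so the check is one of logic, followed by a rough count.

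**Inputs, all from Table 8-3.** S is systolic and D diastolic pressure in mm Hg; patients are asymptomatic.

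- Grade 3 by pressure: S ≥160 or D ≥100.
- Release as written: D ≤90.
- Release with a systolic condition added: S <160 and D ≤90.
- Stricter alternative, for comparison: S ≤140 and D ≤90.

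| Reading | Grade 3? | Written release | With S <160 | With S ≤140 |
|---|---|---|---|---|
| 175/84 | yes, systolic | met | not met | not met |
| 165/95 | yes, systolic | not met | not met | not met |
| 150/104 | yes, diastolic | not met | not met | not met |
| 150/84, after treatment | no, Grade 2 range | met | met | not met |

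The written rule and the S <160 rule differ only in the first line. More generally, take every whole-number pair with S from 160 to 199 and D from 60 to 90: 40 × 31 = 1240 pairs. All 1240 trigger the hold, and all 1240 already meet the written release. With S <160 added none does, since each has S ≥160. The gap is therefore exactly S ≥160 with D ≤90 and no symptoms.

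**Is a systolic release given elsewhere?**

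- Table 7-1 (Section 7) holds Grade 3 toxicities until Grade 2 or lower, which here would mean S <160. Its title excludes hypertension.
- The exclusion criteria (Section 5) call hypertension uncontrolled above 140 systolic or 90 diastolic on repeated measurement despite optimal treatment. The Hypertension text uses the same limits for when a patient must contact staff. Neither governs the release of a hold.

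So no systolic release is stated.

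**Which value fits the table?** S <160 is the Grade 2 boundary. A release at S ≤140 would keep a patient at 150/84 on hold, although an asymptomatic patient first seen at 150/84 continues dosing under the Grade 2 row.

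**How many patients?** Section 1, Clinical Experience, gives 7% grade 3 or higher hypertension on regorafenib in CORRECT. Assume that rate here: 0.07 × 60 = 4.2, about 4 patients. Let f be the share who are asymptomatic with D ≤90, which the documents do not give. The affected number is 4.2 × f: 0 at f = 0, 2.1 at f = 0.5 and 4.2 at f = 1.

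**The case against.** The strongest reply is that the row already responds to systolic pressure. It calls for antihypertensives to be started, increased or added. Its step-down speaks of blood pressure without restricting it to diastolic, and recurrent Grade 3, which includes systolic ≥160, brings a further reduction. Section 8 leaves hypertension management to local standards, describes the reductions as suggestions, and prefers medical control to dose modification. Section 7 lets sites follow institutional practice on dose modification.

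All of that stands, and it limits the point to the release of the hold and the stated aim. It does not remove the point. The step-down governs dose level, not when dosing may resume. The drug treatment is directed at a diastolic aim that these patients already meet. Local practice permits a systolic criterion without stating one.

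A reader might infer more than the documents support:

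- *That controlled blood pressure has no meaning in the protocol and should be set at <160/≤90 in the step-down and footnote b.* The exclusion criteria already treat systolic >140 or diastolic >90 as uncontrolled. A patient at 158/88 would count as controlled under <160/≤90 and could be re-escalated, which would loosen safety.
- *That readings are 28 days apart as soon as the weekly checks of the first 8 weeks end.* Section 4 moves to 4-weekly visits after cycle 2, but the Table of Assessments appears to mark weekly blood pressure in cycles 3 and 4. Only the interval after cycle 4 is settled.
- *That a wrong cross-reference is part of the defect.* The text says "If necessary, Table 8-4 outlines suggested dose reductions", and Table 8-4 is the transaminase table. That is a clerical slip.

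The Grade 2 row also has a diastolic-only aim, and its hold for symptomatic patients has a diastolic-only pressure condition. Asymptomatic Grade 2 patients are not held, so the gap described here does not arise there. The third Grade 3 trigger, the need for more treatment, is also outside this point.

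**Conclusion.** The point holds in this limited form. For an asymptomatic patient with systolic ≥160 and diastolic ≤90, the Grade 3 hold has no required duration, and dosing may resume at the same level while the patient is still Grade 3. Symptomatic patients are still held until symptoms resolve, and those with diastolic >90 are held until it falls.

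The logic rests on the table alone. The size rests on an assumed rate from a trial of all ages at 160 mg. This trial starts older patients at 120 mg, so its rate could differ either way; 0 to about 4 of 60 is an order of magnitude, not a bound.

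Nothing here changes the grading of the event, the primary endpoint, the sample size or the analysis. A reader who infers a threat to the trial's main result would be going beyond the documents. It is a safety instruction that fails for one of its own triggers, and it should be corrected.

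**What to change.** In the Grade 3 row of Table 8-3, insert *systolic BP <160 mm Hg and* before the diastolic condition in the release, keeping the symptom clause. Add a systolic component to the Grade 3 treatment aim. The clinical team should choose that value; the protocol uses 140 in the exclusion criteria and in the patient-contact rule. The aim may be lower than the release value.

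Leave the wording on controlled pressure in the step-down and in footnote b unchanged.

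The cost is one table edit in an amendment, with no new measurements. Holds would be slightly longer for a few patients, and some whose systolic pressure stays at 160 or above for more than 4 weeks would go off protocol therapy under footnote a.

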### Liver Function Abnormalities

For patients with observed worsening of liver tests considered related to regorafenib (i.e. where no alternative cause is evident, such as post-hepatic cholestasis or disease progression), the dose modification and monitoring advice in Table 8-5 should be followed.

Regorafenib is a UGT1A1 inhibitor. Mild, indirect (unconjugated) hyperbilirubinemia may occur in patients with Gilbert’s syndrome.

Table 8-4: Dose Modification/interruption for alanine aminotransferase and/or aspartate aminotransferase increases related to study drug

Increases in ASL/ALT (per NCI-CTCAE v 4.0)	1st Occurrence	Restart	Recurrence
AST and/or ALT < 5 X ULN (<Grade 3)	Continue dosing, with weekly monitoring of liver function until transaminases return to < 3 X ULN (< Grade 1) or baseline.		
ALT and/or AST > 5 X ULN (> Grade 3)	Interrupt dosing, with weekly monitoring until transaminases return to < 3 X ULN or baseline.	If the potential benefit of reinitiating regorafenib is considered to outweigh the risk of hepatotoxicity: reduce 1 dose level and measure transaminases weekly for at least 4 weeks.	Discontinue
ALT and/or AST > 20 X ULN (> Grade 4)	Discontinue		
ALT and/or AST > 3 X ULN (> Grade 2) with concurrent bilirubin > 2 X ULN	Discontinue treatment and measure transaminases weekly until resolution. Exception: subjects with Gilbert's syndrome who develop elevated transaminases should be managed as per the recommendations outlined above for ALT/AST elevations.		

